Organ transplant in last six months	
Bariatric/ gastric bypass surgery, gastric sleeve surgery, or gastric balloon procedure in last six months	

Stroke, heart attack, heart surgery, or hospitalization for congestive heart failure in the past three months	
Other serious health issues or personal concerns that could prevent participant from completing study	

Patients of Michigan Medicine with U-M Premier Care health insurance (either because they are U-M employees or dependents of U-M employees) will be eligible to participate. The U-M has nearly 50,000 diverse employees (25% minority and 60% female) across three campuses. Nearly 75% of U-M employees with U-M health insurance choose Premier Care for their coverage.

Premier Care currently covers the online DPP offered by the company Omada at no cost to plan members with prediabetes. Premier Care also covers metformin as a Tier one (i.e., lowest co-pay) medication.

Recruitment

We will recruit 380 adults meeting the criteria in Table 1. Because the criterion of a certain A1c value range is verified after a participant is consented, we may need to enroll up to 500, with up to 120 being screen failures due to their baseline A1c value being outside of the prediabetes range. We will closely monitor recruitment and adjust our approaches if needed (with IRB amendment approval) to ensure we successfully reach our recruitment targets.

We conservatively estimate that at least 10,000 of the ~33,000 Michigan Medicine patients with U-M Premier Care insurance will meet these criteria. Patients will need to have one of the three insurance plans listed in Table 1 above to ensure coverage of the DPP and low cost-sharing for metformin. Exclusion criteria will include conditions that would make participation in a program to prevent T2DM unfeasible (e.g., inability to consent or illiteracy), inapplicable (e.g., prior diagnosis of T2DM, does not meet an eligibility requirement of the online DPP) or potentially unsafe (e.g., alcohol or opioid dependence, serious psychiatric diagnoses, intensive cancer treatment).

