Data pull and outreach. We will use queries of the Michigan Medicine electronic health record (EHR) to identify patients who meet the inclusion a subset of the criteria in Table 1. The A1c must have been completed at least 30 days ago and less than 12 months ago and have a value from 5.7% to 6.4%, inclusive, or not have had an A1c test in the last year. The list of patients will be reviewed to remove any patients who are not eligible because they participated in the pretesting of study intervention materials (10-30 patients). The remaining patients will be mailed (and/or emailed, when email is listed in health record) a two-sided 5x8 card, in a brightly colored envelope, that describes the study. To protect privacy, the envelope will have the University of Michigan Medical School name, return address, and the block "M," and in the bottom left corner, the text, "Chance to participate in a research study that could benefit you and your health!" On the recruitment card and email, recipients are given the chance to "opt-out" of any further communications about the study by emailing or calling the provided contact information. The email message will contain similar text and photographs as the mailed card, but exact layout will be modified to fit the communication mode.

Website on Qualtrics. The postcard and email direct them to a website hosted in Qualtrics that first asks if they received a mailed card or email about the study that was addressed to them. We ask this question because we anticipate some interested potential participants going to the website after hearing about the study from family and friends who we contact directly.

If they respond that they *did* receive a postcard or email addressed to them, they are taken to pages with more information about the study, contact information for study staff so potential participants can ask questions, and a question about their interest that, if answered affirmatively, takes them to the W2H platform so that they can begin the screening process.

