meaning. Good illustrative statements will be captured verbatim and indicated as such. Notes will be stored in a secure study folder on a departmental shared drive. Interview notes will be coded and analyzed using NVivo software. A code book will be developed beginning with the key domains from the interview guide and using an iterative process among three study staff and PI, with additional codes and subcodes added to account for details that emerged during interviews. The same four individuals will independently code four set of notes and will discuss concordance (Hemmler et al., 2022) to resolve discrepancies in coding via a consensus process. If the study team determines that a high level of consistency in coding had been established, then the sets of notes will be coded independently, with coders applying a “flag for review” code to any sections of text where the coder would like confirmation of a code via team review. If consistency in coding is not established after the group codes four sets of notes, more notes will be coded until consistency in coding is established. The codebook will be revised as needed to reflect new codes that emerge, with notes being recoded as needed. Once coding is complete, the four study team members will independently review key code reports and discuss interpretation of findings. Findings may be used to assist in interpreting study outcomes, improve the program itself, and to identify potential facilitators of and barriers to adoption, implementation, and sustainability. In reports and manuscripts, all data will be deidentified.

9. External controls data. Prior to conducting interviews with the key stakeholders described above as data source #7, we will obtain data that will allow us to share with those interviewed a comparison, between the EUC arm and similar patients who had no intervention, of changes in weight and HbA1c over approximately twelve months. Data will be of patients matching the same initial eligibility criteria that were used for the data pulls for recruitment. Patients will be excluded if they participated in the study, declined to participate after a recruitment call, were unable to reach for recruitment, or were ineligible as determined by screening. Variables provided will be: coded identifier, height, age, sex, race, ethnicity, and both weight and HbA1c with corresponding measurement dates.

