Measures taken to protect privacy and confidentiality are described in the *Privacy and Confidentiality Measures* section of this protocol.

Strategies to Maximize Retention and Data Collection. Participants will receive \$50 when they complete each assessment consisting of the online survey, weigh-in, and A1c test. They will also receive email, text messages, and phone calls to remind them to complete these tasks. We used this approach to limit attrition rates to 2% at 12 weeks in our pilot study and to less than 10% at nine months in two previous trials.^{39,41}

Statistical Design

Sample Size

Based on data from previous studies, in the Enhanced Control Arm we anticipate a mean 12-month absolute HbA1c change (defined as the 12-month measure minus the baseline measure) of 0.0%, a mean 12-month absolute HbA1c decrease of 0.2% in both the Financial Incentives Arm and the Tailored Messages Arm, and a mean 12-month absolute HbA1c decrease of 0.4%

in the Combo Arm. Assuming a 0.4% standard deviation for 12-month HbA1c change in each arm and using an α of 0.017 to adjust for three main comparisons, 85 subjects per arm will provide 99% power to detect the difference between the Financial Incentives Plus Tailored Messages and Enhanced Control Arms (H1a), and 80% power to detect differences between the Combo Arm and the Tailored Messages Arm and the Financial Incentives Arm (H1b). With this sample size, we will also be able to detect meaningful differences (Cohen's d of 0.5 or larger) in secondary outcomes of weight, months of engagement in a Diabetes Prevention Program (DPP), months of taking metformin, and months of engagement in a DPP or taking metformin. To account for possible attrition we have conservatively inflated our sample size by 10% and will enroll 380 participants.

Analysis Plans

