
that will be adjusted to current dollars using medical and pharmaceutical components of the Consumer Price Index. Our cost analysis will also estimate the costs of delivering each study arm, including costs associated with financial incentives and use of the W2H platform.

Sensitivity analyses will be used to examine the impact of using different cost estimates. We will provide stakeholders from Michigan Medicine, BCN, and U-M MHealthy with estimates of the costs of sustaining each approach.

Later in the study, we will develop a detailed plan to evaluate the domains of RE-AIM. Once the plan is developed, we will submit an amendment to IRB for approval.

Aim 4: Compare 12-month changes in HbA1c and weight in the Enhanced Usual Care (EUC) arm to similar patients who received no intervention. Patients receiving no intervention (external controls) will be matched or adjusted for the following characteristics: age, sex, race, ethnicity, and baseline values of BMI, weight and HbA1c. We will use an OLS regression model with 12-month change in HbA1c as the response variable. This model will include an indicator for the EUC (reference is external control), stratification factors, baseline HbA1c values, number of months between two measurements, and any baseline measures that are predictive of missing 12-month data. We will use similar, separate OLS regression models to compare 12-month changes in weight.

Privacy and Confidentiality Measures

Privacy: A potential risk of participation is a breach of a participant's privacy, in which their participation in the research is disclosed to an individual or entity the participant did not wish to have this knowledge. This risk is less serious and lessened in likelihood by collection of informed consent and survey data through the secure W2H web platform.

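### Aim 4 compares trial volunteers with non-enrolled patients using baseline data from one time point; the listed motivation and income terms cannot be fitted for controls, and no pre-baseline check is planned

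*Combined protocol and SAP*

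**What the plan says.** Specific Aims describes Aim 4 as exploratory. It was added once the outcome analyses had shown the EUC arm (the Enhanced Control Arm of the Randomization section) doing best, and its result is meant as context for the staff interviewed under Aim 3.

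Analysis Plans, Aim 4, matches or adjusts external controls on age, sex, race, ethnicity and baseline BMI, weight and HbA1c. The regression is then given as: "This model will include an indicator for the EUC (reference is external control), stratification factors, baseline HbA1c values, number of months between two measurements". Baseline measures that predict missing 12-month data are added.

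Measures and Data Collection, item 9, lists what will be obtained for controls: "coded identifier, height, age, sex, race, ethnicity, and both weight and HbA1c with corresponding measurement dates". Controls must meet the initial data-pull criteria. Trial participants, people who declined after a recruitment call, people who could not be reached and people screened out are removed.

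The Randomization section defines the stratification factors as household income and autonomous motivation, both taken from the baseline survey.

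On HbA1c, Data pull and outreach says: "The A1c must have been completed at least 30 days ago and less than 12 months ago", with a value in the prediabetes range. It also admits patients with no test in the last year. Enrollment then requires a new in-range test after consent, and that test is the trial baseline.

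**The concern.** Before randomization, EUC participants had answered outreach, worked through consent questions, given blood, completed a survey and sent a weight reading. A control had only to meet the record criteria and have values at two dates. The two groups may therefore differ in motivation, or in whether they were already improving or worsening, and demographics with one set of baseline values need not capture either.

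The protocol itself treats motivation as important. Its background reports that employees with higher motivation were more likely to take up prevention. Its pilot volunteers averaged 37.6 on a scale from 6 to 42, with 18 at the maximum. The trial stratifies on this measure.

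If the groups differ in this way, the Aim 4 contrast mixes the effect of volunteering with the effect of the programme. Staff asked about sustaining the programme would be shown that mixture.

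**Working it through.** **Can the model be fitted?** Set the two lists side by side. The model needs income and autonomous motivation. The control extract holds an identifier, height, age, sex, race, ethnicity, and dated weight and HbA1c. Neither stratification factor is there, and their only stated source is a survey that controls never took. The term cannot be estimated. What remains is demographics, baseline body size and HbA1c, the measurement interval, and any missingness predictors that controls also have.

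**Is the HbA1c entry rule the same?** EUC participants recruited on a record value had to be in range twice: in the record and again after consent. Controls face the data-pull criterion only. A single in-range value regresses further towards the population mean than one confirmed by a second test.

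**The plan's own figures first.** The Sample Size inputs are "Assuming a 0.4% standard deviation for 12-month HbA1c change in each arm", "using an α of 0.017 to adjust for three main comparisons", 85 per arm, and a 0.2-point difference between the Combo Arm and each single-component arm (0.4 against "a mean 12-month absolute HbA1c decrease of 0.2% in both the Financial Incentives Arm and the Tailored Messages Arm"). Sidedness is not stated; two-sided is assumed.
- SE = 0.4 × √(1/85 + 1/85) = 0.0614; critical value 2.387.
- Power = Φ(0.2/0.0614 − 2.387) = Φ(0.873) = 0.81, or 0.80 with the noncentral t. This matches the stated 80%.

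**What a residual bias would do.** Aim 4 gives no number of controls and no power. Assume 85 EUC completers, SD 0.4 and no true effect. With m controls, SE = 0.4 × √(1/85 + 1/m). The probability of a false difference is Φ(b/SE − 2.387) + Φ(−b/SE − 2.387), where b is an assumed bias.

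| m | SE | b = 0.05 | b = 0.10 |
|---|---|---|---|
| 85 | 0.0614 | 5.9% | 22.5% |
| 340 | 0.0485 | 8.8% | 37.3% |
| 1,000 | 0.0452 | 10.0% | 43.1% |

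The nominal rate is 1.7%. More controls shrink the SE but not the bias, so the error rate rises.

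**What a prior value can and cannot do.** A simulation with no EUC effect used assumed between-person SD 0.3, within-person SD 0.2 and population mean 5.5 to 5.9. EUC participants were in range twice; controls were in range at baseline. Negative values favour EUC. The placebo column compares change up to baseline, using only controls who were also in range twice.

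| Scenario | Baseline only | Plus prior HbA1c | Placebo |
|---|---|---|---|
| Double test only | +0.015 to +0.055 | about 0.00 | about 0.00 |
| Motivation acts after baseline only | −0.04 to −0.07 | about −0.09 | about 0.00 |
| Acts before and after | −0.08 to −0.10 | about −0.12 | about −0.04 |
| Acts before only, then persists | +0.02 to −0.02 | about −0.05 | about −0.04 |

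In the second row, the prior value appears to make matters worse. What it does is remove an offsetting error: at mean 5.5, −0.091 + 0.055 = −0.036, close to the baseline-only −0.038. In the last row most of the shift has the same source, but the prior value also adds about −0.01 of its own.

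**The case against.** The strongest reply is that Aim 4 is openly labelled exploratory, its late addition is disclosed, and no primary or secondary conclusion depends on it. That stands, and it limits the severity.

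The plan also does more than a hurried reading suggests. It lists three baseline measures, the measurement interval and missingness predictors, and it names the stratification factors. That stands too, except that the stratification factors are not available for controls.

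Three stronger readings are tempting, and the documents do not support them:
- A reader might divide the 380 target by "at least 10,000 of the ~33,000 Michigan Medicine patients with U-M Premier Care insurance will meet these criteria" and call 3.8% an uptake rate that proves strong selection. It is a fixed target over an estimated pool, and the number invited is not given.
- A reader might call the controls unselected. Decliners, unreachable and screened-ineligible patients are removed, so the pool probably leans towards people never called, some of whom would have volunteered.
- A reader might expect prior values to settle the matter. In the simulation they correct the double test, whose bias runs against EUC, and the placebo flags volunteers already improving. They neither detect nor remove motivation that acts only after enrolment.

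It is also fair to say that earlier HbA1c values are not assured. Patients with no test in the last year could be recruited, and nothing confirms that values before the control baseline exist or will be pulled.

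**Conclusion.** The concern holds as a minor point. Two parts follow from the text alone: the stratification term cannot be fitted with the data requested for controls, and no pre-baseline comparison or other check on volunteer selection is planned. The different HbA1c entry rule also follows from the text, for participants recruited on a record value.

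The size is illustrative. The 6–10% and 22–43% rest on assumed biases of 0.05 and 0.10 points, which have no source in the documents, and on 85 completers, SD 0.4, two-sided 0.017 and 85 to 1,000 controls. The simulated values rest on their own assumed variances and on the control's in-range value serving as its baseline.

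A reader might infer that the good EUC result is merely volunteering. The documents do not show that: volunteer motivation would probably favour EUC, the double test works against it, and neither has been measured.

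**What to change.** Reconcile item 9 of Measures and Data Collection with Aim 4: either drop the stratification factors from this model or state where the control values will come from. Then extend the extract back 12–24 months for both EUC participants and controls, and:

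1. Run the same model on pre-baseline change in routine weight, and in HbA1c where two earlier values exist, as a placebo outcome reported with its confidence interval. For HbA1c, apply the same in-range rule to both groups; otherwise the entry rule itself creates a difference.
2. As a sensitivity analysis among patients with the data, add a prior HbA1c and weight value to the adjustment set, and show this beside the planned estimate. It corrects for the double in-range test.
3. Present Aim 4 to interviewed staff as a descriptive comparison that includes volunteer selection, whatever the placebo shows. A near-zero placebo is not clearance.

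The cost is a longer look-back, a matching historical pull for EUC participants and a few more model runs. The checks will cover only patients with earlier values, so report how many that is in each group.

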Measures and Data Collection

We will collect data from nine sources. The first three comprise participant assessments that will be completed at baseline, 6, and 12 months.

1. HbA1c. To objectively measure our clinically meaningful primary outcome of change in HbA1c, participants will have their HbA1c measured at a Michigan Medicine lab. The A1c completed as part of the enrollment process to confirm eligibility will also be used as the baseline A1c value. If enrollment is delayed and three or more months lapse between the A1c measure and final enrollment steps, the participant will need to get another A1c test completed to be used for the baseline measure.
2. Weight. Participants will be shipped a digital body weight scale after the participant is fully enrolled. Participants will be given instructions on how to use their scales to weigh themselves (use of scale, time of day, type of clothing) and how to submit a photo of the scale's display of their weight to the study in the secure Way to Health platform. See final section of protocol beginning on page 19 for details on privacy, confidentiality, and security measures. Participants will keep the scale after their study participation ends.
3. Survey. Participants will complete online surveys in the W2H platform at three time points. None of these measures are outcome measures; rather, they describe the participant population, are potential moderators or mediators, or provide insight into the participants' experiences in the study. Survey domains and measures are shown in the table below:

Domain	Survey Month			Measures
	0	6	12	
Demographics	X			Age, gender, race/ethnicity, job, education, household income, whether diagnosed with prediabetes and time since diagnosis, diagnosis of comorbidities, provider clinic and name, people in household, work status
Roles, values, strengths	X	X		Measures from our prior studies ⁶⁷
Physical Activity	X	X	X	International Physical Activity Questionnaire
Eating habits	X	X	X	Rapid Eating Assessment for Participants
Future orientation	X			Consideration of Future Consequences Scale ³³
Health causality orientation	X	X	X	Health Causality Orientations Scale
Autonomous/controlled motivation	X	X	X	Treatment Self-Regulation Questionnaire ¹⁵⁷
Incentive salience		X	X	0 to 10 rating of incentive importance from our prior studies ^{39,41}
Perceived coercion	X	X		Financial Incentive Coercion Assessment Questionnaire ¹⁷²

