Process to provide incentives. Deposits to the participant's ClinCard will be made electronically through a University of Pennsylvania-approved partnership with Greenphire. Greenphire's ClinCard program is HIPAA-certified. Social security numbers, names, addresses, and date of birth for all persons to whom incentive payments are sent are kept within the ClinCard system. Each year, Accounts Payable at the University of Pennsylvania securely downloads a report from Greenphire that includes anyone paid in the previous calendar year. That data is kept secure and only the data of people that earned \$600 or more is uploaded to a secure third party vendor to process 1099's.

Transfer of body weight data for assessments. Participants will measure their body weight using a digital scale in their home that the study will have shipped to them. Upon receipt of the scale, participants will receive instructions on how to weigh themselves, take a photo of their weight on the display, and submit the photo to the study by texting the photo to the study's number in the Way to Health system.

Transfer of prescription fill data. Each month, study staff will upload to MiShare a file containing the prescription drug plan ID numbers of all current study participants. A member of the University of Michigan's Prescription Drug Plan team will run a query, based on the prescription drug plan ID provided, for the claims extract of the metformin claims for the previous month for study participants only. The results will be uploaded to MiShare to share with select study staff, and study staff person will download and store the data in the study folder.

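### Aim 4 compares home-scale weight change in the EUC arm with what appear to be record weights in external controls, so a source offset that shifts between readings could mimic or hide an EUC benefit

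*Combined protocol and SAP*

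**What the plan says.** **EUC weights.** Under Privacy and Confidentiality Measures (transfer of body weight data), "Participants will measure their body weight using a digital scale in their home". Measures and Data Collection, item 2, says the scale is shipped by the study. Participants are instructed on its use, on time of day and on clothing, and are told "how to submit a photo of the scale's display of their weight to the study in the secure Way to Health platform". Aim 4 does not name the weight source for the EUC arm (called the Enhanced Control Arm elsewhere). The study's home-scale measure is the natural reading.

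**Control weights.** Measures and Data Collection, item 9: "Data will be of patients matching the same initial eligibility criteria that were used for the data pulls for recruitment". The variables supplied are "coded identifier, height, age, sex, race, ethnicity, and both weight and HbA1c with corresponding measurement dates". No setting or device is given. The Recruitment section says those pulls query the Michigan Medicine electronic health record.

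**Analysis.** Analysis Plans, Aim 4, matches or adjusts for demographics and for baseline BMI, weight and HbA1c. The HbA1c model has an EUC indicator, stratification factors, baseline value, months between the two measurements, and predictors of missingness. For weight: "We will use similar, separate OLS regression models to compare 12-month changes in weight". There is no restriction to like-for-like weights and no sensitivity analysis on source. Specific Aims labels Aim 4 exploratory, added after the EUC arm was seen to do best, and intended to give context to staff interviewed under Aim 3.

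**The concern.** One group is weighed at home on a study scale, following instructions, and reports its own reading. The other was given no study scale and no instructions, and its weights were probably taken in routine care. Every EUC weight would come from one source and every control weight from the other, so source and group are the same variable. A source term could not be estimated even if it were added, and baseline values and interval length do not stand in for it.

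Weight is one of only two Aim 4 outcomes, and the result will be shown to staff who are being interviewed about implementation and sustainability. If the gap between sources changes over the year, they could be shown a programme effect that is partly an artefact, or miss one that is real. Participants' HbA1c is measured at a Michigan Medicine laboratory and does not raise the same problem.

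**Working it through.** The plan gives no sample size, SD or effect size for Aim 4, so there is no stated figure to reproduce. The check is how much of a source difference survives in the planned analysis.

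**Step 1: raw change.** Let d0 and d1 be the record-minus-home offset at baseline and at 12 months. With no true group difference, the EUC-minus-control difference in measured change is −(d1 − d0). If d1 = d0, it is zero.

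**Step 2: baseline adjustment.** If weight change has slope β on baseline weight, a constant offset d leaves about β × d, because the two baselines are on different instruments. With assumed slopes of −0.02 to −0.10 and offsets of 0.5 to 2 kg, its size runs from 0.02 × 0.5 = 0.01 kg to 0.10 × 2 = 0.20 kg.

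**Step 3: simulation.** OLS of weight change on group and baseline weight, no true difference. All inputs are assumed: 85 EUC participants, 500 controls, baseline SD 18 kg, change SD 5 kg, reading-error SD 0.5 kg, 3,000 replicates. Monte Carlo standard error is 0.011 kg. Negative values favour EUC.

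| Offset at baseline → 12 months (kg) | Slope | Raw difference (kg) | Adjusted difference (kg) |
|---|---|---|---|
| 0 → 0 | −0.05 | 0.014 | 0.013 |
| 1 → 1 | −0.05 | −0.011 | −0.060 |
| 2 → 2 | −0.05 | −0.016 | −0.116 |
| 2 → 2 | −0.10 | −0.007 | −0.206 |
| 1 → 2 | −0.05 | −0.983 | −1.030 |
| 1 → 0.5 | −0.05 | 0.481 | 0.432 |
| 1.5 → 0.5 | −0.05 | 0.982 | 0.906 |

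Raising the record weights' error SD to 1.5 kg with a constant 1 kg offset gives −0.064 kg adjusted, so extra noise alone adds almost no bias. A constant offset nearly vanishes. A shifting one passes through almost whole, with the sign of the shift deciding which group it favours.

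**Step 4: what a surviving bias would do.** Assumed: 85 EUC participants, 2,000 controls, SD of change 5 to 7 kg, and the plan's α of 0.017 (two-sided critical value 2.387) applied to Aim 4.

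SE = SD/√85 × √(1 + 85/2000). SD 5 gives 0.542 × 1.021 = 0.55 kg; SD 7 gives 0.759 × 1.021 = 0.78 kg.

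Rejection probability with bias b and no true effect = Φ(b/SE − 2.387) + Φ(−b/SE − 2.387):

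| Bias | SD 5 kg | SD 6 kg | SD 7 kg |
|---|---|---|---|
| 0 | 1.7% | 1.7% | 1.7% |
| 0.5 kg | 6.9% | 5.2% | 4.2% |
| 1.0 kg | 28.1% | 18.9% | 13.6% |

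The 0.5 and 1.0 kg values are inputs, not estimates. The table shows what such a bias would do, not that one exists.

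**Step 5: could the offset shift?** Nothing in the documents shows that it does, and nothing rules it out. Item 9 describes changes over roughly a year and gives no date window or rule for choosing among several record weights. Season and clothing can therefore differ between a control's two readings, and the months-between covariate measures interval length, not season. On the EUC side, readings are self-reported, and the later one follows a year of prevention messages.

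**The case against.** The strongest reply is that the outcome is within-person change and each group appears to use one source throughout, so most of a source difference cancels. That is correct, and it makes the different baseline instruments a minor matter. Season and clothing bias the mean only if they shift systematically; otherwise they add noise. The model also adjusts for interval length. Aim 4 is exploratory and post hoc, and the same-source analysis has its own weakness: it replaces instructed readings taken at set assessments with opportunistic ones, for those EUC participants who have them. For that reason it should stand beside the home-scale analysis and not replace it.

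The following stronger readings are tempting, but the documents do not support them:

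- That part of any observed difference is measurement source. This needs a shifting offset, which is possible but not shown.
- That the artefact would favour EUC. The sign depends on the shift, and two of the three shifting scenarios above count against EUC.
- That participants pick a favourable reading. The text describes weighing, photographing and submitting. The $50 payment is for completing the assessment, whatever the value.
- That control weights are known to be clinic weights. This is inferred from the record-based data pull.

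That a control has a follow-up weight only after a care contact is a selection issue, separate from source.

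What stands is that source coincides with group, that adjustment cannot separate them, and that the plan does not mention it.

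**Conclusion.** The concern holds as an unaddressed possible bias in one exploratory, non-randomised comparison. A constant source offset is of little consequence: about 0.01 to 0.20 kg after baseline adjustment, for assumed offsets of 0.5 to 2 kg. A shift of 0.5 to 1 kg between readings would move the estimate by about 0.4 to 1.0 kg either way. On the sample sizes and SDs assumed above, a surviving bias of 0.5 to 1.0 kg would raise a 1.7% false-positive rate to between 4.2% and 28.1%. The actual size and direction are unknown. The conclusion rests on two inferences: that the EUC analysis uses the home-scale weights, and that control weights come from the health record.

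A reader might infer that the trial's randomised weight results are also in doubt. They are not, because all four arms use the same method.

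**What to change.** A cheap improvement, in three parts:

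1. State in Aim 4 the source of the weights in each group.
2. Add EUC participants (about 380/4 = 95) to the planned extract. They have Michigan Medicine primary care providers, so record weights should exist for many of them. Write down one rule for choosing baseline and follow-up weights by date, since none is given, and apply it to both groups.
3. Report this same-source comparison beside the home-scale one. Attribute a weight difference to the EUC programme only if the two agree, and say beforehand what counts as agreement. Agreement would remove source as an explanation, but not the other limits of a non-randomised comparison.

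The cost is a small addition to an extract already planned, plus an IRB amendment. Some EUC participants will lack record weights near both dates, so this analysis will be less precise. Who has a recorded weight may also differ between groups, partly because the programme promotes metformin and sends chart updates to primary care. Report the number and baseline characteristics of those with and without usable record weights in each group.
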